6.5.1.2 Lymphoblast PD-L1 and PD-L2 expression by Western Blot (UCSD)

Bone marrow aspirate samples for FACS of lymphoblasts and PD-L1 and PD-L2 expression by Western blotting will be collected at the following time points and shipped to the laboratory of [name], PhD:

At screening
Cycle 1 Day 14

Cycle 1 Day 29 +8 days

In the case of a dry tap, a core biopsy is to be collected.

Complete Sample Collection CRF (Appendix F) for each shipment. Email the completed Sample collection CRF prior to shipment to [contact]

- Make a copy of the form to include with the sample(s)
- Retain the original at the site for your records

Email a de-identified (redacted) pathology report(s) if available. Write the study ID on the top of each page of the pathology report.

Samples to be shipped overnight to the [name] Laboratory for processing and analysis:

[name], PhD
Department of Pathology
University of California San Diego
[name]
[name]
[name]
Ph: [contact]

Email: [contact]

6.5.1.3 T-cell subsets, PD-1 and PD-L1 expression studies by Flow Cytometry

Bone marrow aspirate and peripheral blood samples for flow cytometry for T-cell subsets, PD-1 on T-cells and PD-L1 on lymphoblasts along with appropriate patient-specific lymphoblast markers.

Minimum flow cytometry panels as follows:

Peripheral blood T-cells:

Panel 1 (identification.activation panel) - live/dead stain, CD3, CD4, CD8, CD16, CD56, OX40, CD137, PD-1, LAG-3, TIM-3

Panel 2 (Treg panel) - live/dead stain, CD4, CD25, FoxP3 (intracellular)

Panel 3 (NK cells) - live/dead stain, CD3, CD4, CD8, CD16, CD56, IFN-g (intracellular), granzyme-B (intracellular)

Bone marrow lymphoblasts: PD-L1, CD19, CD10*, TdT*, 7-AAD

(Note: *lymphoblast markers to be selected based on initial immunophenotype and may also include CD34, cCD22, sCD22, CD24, Pax5, CD79a)

Aspirate samples will be sent for testing at the following time points:

At screening

Cycle 1 Day 14

Cycle 1 Day 29 + 8 days

Cycle 2 Day 29 + 8 days

3-5 mL of bone marrow aspirate and 5 mL peripheral blood to be collected in EDTA (lavender-top) tube and be sent same day by hand delivery or overnight shipping to the laboratory of [name], PhD:

[name], PhD
Department of Pathology
University of California San Diego
[name]
[name]
[name]
Ph: [contact]
Email: [contact]

In the case of a dry tap, a core biopsy is to be collected.

6.5.1.4 Serum cytokine assays

Peripheral blood Serum Cytokine assays samples will be collected at the following time points in Cycle 1:

Day 1 (prior to blinatumomab)
Day 2 (24 +/- 2 hours after blinatumomab start)
Day 3 (48 hours +/- 2 hours after blinatumomab start)
Day 8 (prior to blinatumomab 28 mcg/day dose)
Day 9 (24 +/- 2 hours after blinatumomab dose increase on Day 8)
Day 10 (48 hours +/- 2 hours after blinatumomab dose increase on Day 8)
Day 15 (prior to pembrolizumab)
Day 16 (24 +/- 2 hours after pembrolizumab Day 15 dose)
Day 17 (48 +/- 2 hours after pembrolizumab Day 15 dose)
Day 21

This study will utilize the Cytokine Human 10-plex panel for Luminex® Platform which measures levels of GM-CSF, TNF- α , IL-2, IL-1 β , IL-4, IL-6, IL-8, IFN- γ , IL-10, IL-5.

Peripheral blood to be collected in 1-10mL EDTA tube. Sample to be processed at 1200g for 10min and the plasma stored at -70C. Samples may be batch shipped after collection of all samples for each patient have been collected. Please ensure that a completed CRF form (appendix F) is included with each sample.

Samples to be shipped to UCSD overnight on dry ice.

Study Coordinator, BMT Clinical Trials
UCSD Moores Cancer Center
[name]
[name]
[contact]

Samples to be stored at the UCSD Moores Cancer Center Clinical Trials office until analyzed in [name] at UCSD.

6.6 Removal of Subjects from Study Treatment and Study

Patients can be taken off the study treatment and/or study at any time at their own request, or they may be withdrawn at the discretion of the investigator for safety, behavioral or administrative reasons. The reason(s) for discontinuation will be documented and may include:

1. Patient completed study treatment;
2. Patient voluntarily withdraws from treatment (follow-up permitted);
3. Patient withdraws consent (termination of treatment and follow-up);
4. Patient is unable to comply with protocol requirements;
5. Patient demonstrates disease progression;
6. Patient experiences toxicity that makes continuation in the protocol unsafe;
7. Treating physician judges continuation on the study would not be in the patient's best interest;
8. Patient becomes pregnant (pregnancy to be reported along same timelines as a serious adverse event);
9. Development of second malignancy (except for basal cell carcinoma or squamous cell carcinoma of the skin) that requires treatment, which would interfere with this study;
10. Lost to follow-up.

If a research subject cannot be located to document survival after a period of 2 years, the subject may be considered "lost to follow-up." All attempts to contact the subject during the two years must be documented.

7. Measurement of Effect

7.1 Assessment of disease response

7.1.1 Definitions

Evaluable for toxicity. All patients will be evaluable for toxicity from the time of their first treatment on study.

Evaluable for objective response. Only those patients who have measurable disease present at baseline who have received at least one cycle of therapy and have had their disease re-evaluated will be considered evaluable for response. These patients will have their response classified according to the definitions stated below.

7.1.2 Disease Parameters

Measurable disease.

Bone marrow:

Detectable disease by standard morphology, immunohistochemistry, and/or flow cytometry.

M1: <5% lymphoblasts

M2: ≥5% but ≤25% lymphoblasts

M3: >25% lymphoblasts

Minimal residual disease: To be assessed by a minimum of 6-color flow cytometry with each bone marrow aspiration and biopsy on a minimum of 0.5×10^6 mononuclear cells when technically possible.

Peripheral blood:

Detectable disease by standard morphology (peripheral blood smear) and/or flow cytometry.

Extramedullary disease:

Lymph node enlargement: measurable (pathologically enlarged) lesions are lymph nodes with short axis diameter >10 mm except for submental and submandibular nodes which are measurable (pathologically enlarged) if >15 mm in short axis and retropharyngeal nodes which are measurable if >8 mm.

Extramedullary masses outside of lymph nodes: measurable lesions are defined as those that can be accurately measured in at least one dimension (longest diameter to be recorded) as ≥ 20 mm with conventional techniques (CT, X-ray) or as ≥ 10 mm with spiral CT scan. All tumor and lymph node measurements must be recorded in millimeters (or decimal fractions of centimeters).

CNS Disease: Will be assessed by cell count and cytology at screening, with each intrathecal chemotherapy treatment, and at suspicion for new or worsening CNS disease.

Definitions of CNS disease status:

CNS-1: No lymphoblasts in the CSF

CNS-2: WBC <5 /microliter with presence of lymphoblasts in CSF

CNS-3: WBC ≥ 5 /microliter with presence of lymphoblasts in CSF or cranial nerve deficit

If lumbar puncture is traumatic in a patient with circulating blasts and CSF WBC is ≥ 5 cells/mcL in CSF with blasts, calculate the CSF and blood WBC/RBC ratios. If the CSF WBC/RBC ratio is at least two-fold greater than the blood WBC/RBC ratio, then classify as CNS-3; if less than two-fold greater, then it is CNS-2.

Non-measurable disease. All other lesions (or sites of disease), including small extra-nodal lesions (longest diameter <20 mm with conventional techniques or <10 mm using spiral CT scan), are considered non-measurable disease. Bone lesions, leptomeningeal disease, ascites, pleural/pericardial effusions, leukemia/lymphoma cutis, abdominal masses (not followed by CT), hepatomegaly, splenomegaly, testicular masses, gum infiltration, and cystic lesions are all considered non-measurable.

7.1.3 Methods for Evaluation of Measurable Disease

Bone marrow:

Bone marrow aspiration of 2-3 ml should be prepared for standard morphologic evaluation by aspirate smears on glass slides. Additional aspirate (5-10 mL) should be obtained for flow cytometry, cytogenetics (karyotype and *in situ* hybridization), and molecular analyses.

Bone Marrow Aspirate or Biopsy samples to be collected at study specified time points and sent to the University of Washington for MRD analysis (see **Appendix C**). MRD assessment to be done on first pull bone marrow aspirate. If necessary, aspirate needle should be re-directed to obtain first pull aspirate for MRD studies.

This analysis is to be performed on all patients, and billed to their insurance.

Requisition form for samples available in **Appendix C**.

If bone marrow aspirate cannot be obtained (dry tap) or no spicules present in aspirate, 2 bone marrow core biopsies should be obtained for flow cytometry and cytogenetics. Institutional practice supersedes.

Bone marrow core needle biopsy should be 1-2 cm in length for adequate evaluation.

Blood:

Evaluation of peripheral blood should occur by morphologic evaluation of a peripheral blood smear. This should be performed at the time of each bone marrow biopsy and when clinically indicated.

Extramedullary Disease

Lymph node enlargement, tumors:

For patients with a known mediastinal mass or lymphadenopathy or palpable masses on physical exam, FDG-PET/CT scan will be performed with diagnostic CT scans of the chest, abdomen, and pelvis with IV contrast except when contraindicated or felt unsafe by the investigator. When PET-CT not feasible, CT chest/abdomen/pelvis with contrast alone should be performed.

For patients with pathologic lymph node enlargement or tumors, all measurements should be taken and recorded in metric notation using a ruler or calipers. All baseline evaluations should be performed as closely as possible to the beginning of treatment and never more than 14 days before the beginning of the treatment.

The same method of assessment and the same technique should be used to characterize each identified and reported lesion at baseline and during follow-up. Imaging-based evaluation is preferred to evaluation by clinical examination when both methods have been used to assess the antitumor effect of a treatment.

CNS disease:

CSF samples from lumbar punctures should be sent for cell count, total protein, glucose, and standard cytology with every lumbar puncture performed while patient remains on study.

Effusions:

When safe to do so, pleural effusions and ascites should be sampled and analyzed by standard cytology for evidence of disease.

Cytologic evaluation of any effusion that appears or worsens during treatment when the measurable tumor has otherwise met criteria for complete response or stable disease is mandatory to differentiate between complete response and progressive disease.

7.1.4 Response Criteria

Response criteria for bone marrow, blood, CNS disease, and mediastinal disease are from NCCN Guidelines for Acute Lymphoblastic Leukemia, Version 1.2015, 06/11/15.

Response criteria for lymph node and other extramedullary disease are derived from International Working Group revised response criteria for malignant lymphoma [17].

7.1.4.1 Bone Marrow and Blood

Complete Response (CR):

- No circulating blasts or extramedullary disease
- Bone marrow with normal trilineage hematopoiesis and <5% blasts
- Absolute neutrophil count (ANC) >1,000/microliter
- Platelet count >100,000/microliter
- No disease recurrence for 28 days

Complete Response with Partial Hematologic Recovery (CRh):

- As for CR but platelet count >50,000/microliter, hemoglobin >7 g/dL, and ANC >500/microliter

Overall Response Rate (ORR):

- Defined as the sum of the CR rate and CRh rate.

Refractory disease:

- Failure to achieve CR at end of induction

Progressive Disease (PD):

- Increase of at least 25% in the absolute number of circulating or bone marrow leukemic blasts or appearance of new extramedullary disease

Relapsed Disease:

- Re-appearance of blasts in the bone marrow (>5%) or blood or in any extramedullary site after achieving a CR or CRh

Flow MRD Negativity:

- Absence of detectable leukemic blasts above the 0.01% (1×10^{-4}) level by minimum 6-color flow cytometry

7.1.4.2 CNS Disease

CNS Remission:

- Achievement of CNS-1 disease status in a patient with CNS-2 or CNS-3 disease status at diagnosis

CNS Relapse:

- New development of CNS-3 disease status or clinical signs of CNS involvement such as cranial nerve palsy, brain involvement, eye involvement, or hypothalamic syndrome. Whenever possible, clinical signs of CNS involvement without concomitant CSF involvement should be confirmed by biopsy. Otherwise, attribution of CNS symptoms to leukemia/lymphoma and requirement for treatment will be based on investigator judgment.

7.1.4.3 Mediastinal Disease

Complete Response:

- Complete resolution of mediastinal enlargement by CT or if FDG-avid/PET positive prior to therapy, mass of any size permitted if PET negative

Complete Response Unconfirmed (CRu):

- Residual mediastinal enlargement that has regressed by >75% in the sum of the product of the greatest perpendicular diameters (SPD)

Partial Response (PR):

- >50% decrease in the SPD of the mediastinal enlargement

Progressive Disease (PD):

- >25% increase in the SPD of the mediastinal enlargement

No response (NR):

- Failure to qualify for CR, CRu, PR, or PD

Relapse:

- Recurrence of mediastinal enlargement after achieving CR or CRu

7.1.4.4 Nodal Disease

Complete Response:

- Complete resolution of lymph node enlargement by CT or, if FDG-avid or PET positive prior to therapy, lymph node enlargement of any size permitted if PET negative

Partial Response (PR):

- ≥50% decrease in the SPD of up to 6 largest dominant masses with no increase in size of other nodes

Progressive Disease (PD) or Relapse:

- any new enlarged lymph node mass >1.5 cm in any axis, ≥50% increase in the SPD of more than one node, or ≥50% increase in the longest diameter of a previously identified node >1 cm in short axis
- lesions PET positive if FDG-avid or PET positive prior to therapy

No response (NR):

- Failure to qualify for CR, PR, or PD

7.1.4.5 Other Extramedullary Disease (e.g. Spleen, Liver)

Complete Response:

- Complete resolution of disease by CT or, if FDG-avid or PET positive prior to therapy, lymph node enlargement of any size permitted if PET negative

Partial Response (PR):

- $\geq 50\%$ decrease in the SPD of up to 6 largest dominant masses with no increase in size of other masses. If single mass then $\geq 50\%$ decrease in greatest transverse diameter. No increase in size of liver or spleen.

Progressive Disease (PD) or Relapse:

- $> 50\%$ increase from nadir in the SPD of any previous lesions

No response (NR):

- Failure to qualify for CR, PR, or PD

7.1.5 Duration of Response

The duration of overall response is measured from the date that measurement criteria are met for CR/CRh until the first date that relapsed disease is objectively documented.

7.1.6 Relapse-Free Survival

Relapse-free survival (RFS) is defined as the duration of time between objective documentation of CR/CRh and relapse of disease or death in CR.

7.1.7 Overall Survival

Overall survival is defined as the duration of time from start of treatment to death from any cause.

7.2 Safety/tolerability

Analyses will be performed for all patients having received at least one dose of study drug. The study will use the CTCAE version 4.03

(<http://ctep.cancer.gov/reporting/ctc.html>) for reporting of (non-hematologic) adverse events.

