3.2 Secondary Endpoints

3.2.1 CR rate as defined above.

3.2.2 Minimal residual disease (MRD) negativity in subjects achieving a CR or CRh will be defined as less than 0.01% residual lymphoblasts by multiparameter flow cytometry.

3.2.3 2-year relapse-free survival (RFS) will be defined as the time from achieving CR or CRh to relapse defined as the reappearance of lymphoblasts in bone marrow or blood at >5% of cells or reappearance of extramedullary disease.

3.2.4 2-year overall survival (OS) will be defined as the time from starting study therapy to death from any cause.

3.2.5 ORR, CR rate, 2-year RFS, and 2-year OS in the Ph/BCR-ABL1-negative and Ph/BCR-ABL1-positive populations separately.

3.2.6 Allogeneic hematopoietic cell transplantation (HCT) rate in transplant-eligible subjects will be defined as the number of patients eligible for allogeneic HCT as determined by the investigator who actually proceed to transplant.

3.2.7 Safety and tolerability of blinatumomab in combination with pembrolizumab will be defined by treatment-emergent Grade 2-5 adverse events (AEs) defined using NCI CTCAE v4.03 toxicity criteria attributable to study therapy.

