5. TREATMENT PLAN

5.1 Treatment dosage and administration

5.1.1 Treatment summary

The study will be conducted in 2 stages:

Stage 1 is to ensure safety of pembrolizumab in combination with blinatumomab.

Dose Limiting Toxicity (DLT) is defined as a clinically significant adverse event that is considered by the investigator to be probably or definitely related to pembrolizumab or the combination of pembrolizumab and blinatumomab occurring within 42 days of the first dose of pembrolizumab on Day 15 of Cycle 1 as follows:

- Any Grade 3-5 non-hematologic toxicity EXCEPT:
 - Grade 3 cytokine release syndrome that resolves in 7 days or less
 - Grade 3 neurotoxicity that resolves in 7 days or less
 - Grade 3 infections
 - Grade 3 or 4 febrile neutropenia unless deemed by investigator to be definitely related to pembrolizumab
 - Grade 3 or 4 laboratory abnormalities unless they warrant temporary discontinuation of pembrolizumab or permanent discontinuation of blinatumomab (see tables, 5.7.1 and 5.7.2)
 - Grade 3 or 4 lymphopenia
- Any clinically significant toxicity that precludes administration of the next scheduled dose for more than 14 days

If no DLTs are experienced in the first 3 subjects then enrollment will advance Stage 2. If 1 DLT is noted in the first 3 subjects then 3 additional subjects will be enrolled. If no further DLTs are noted in the additional 3 subjects then enrollment will proceed to Stage 2. If 2 or more DLTs are noted at the proposed pembrolizumab dose level and schedule then enrollment will be placed on hold and a dose reduction or schedule change will be considered after discussion of investigators.

The DLT monitoring period will be 42 days starting on Day 15 of Cycle 1. Subjects withdrawing from investigational treatment during the DLT monitoring period for a reason that is definitely unrelated to toxicity of the study agent (e.g. disease progression, patient withdrawal of consent) will be deemed not evaluable for DLT determination and will be replaced. All subjects in Stage 1 will need to complete the DLT monitoring period prior to proceeding with Stage 2.

Stage 2 of the study will include an expansion cohort of up to 21 additional subjects (for a total of 24 subjects) to evaluate the efficacy of the combination of blinatumomab and pembrolizumab.

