5.7 Toxicities and Dosing Delays/Dose Modifications

Any patient who receives treatment on this protocol will be evaluable for toxicity. Each patient

will be assessed for the development of toxicity except cytokine release syndrome (see below, grading/management per Lee et al. Blood 2014) according to the NCI Common Toxicity Criteria for Adverse Events (CTCAE), version 4.03. Dose adjustments should be made according to the system showing the greatest degree of toxicity. As Blinatumomab is an approved treatment for this indication, reducing or withholding pembrolizumab should be considered as the first option in response to a toxicity prior to adjusting the Blinatumomab dosing.

Adverse events (both non-serious and serious) associated with pembrolizumab exposure may represent an immunologic etiology. These adverse events may occur shortly after the first dose or several months after the last dose of treatment. Pembrolizumab and blinatumomab must be withheld for drug-related toxicities and severe or life-threatening AEs as per Tables below. See Section 5.6.1 in Events of Clinical Interest Guidance Document for additional supportive care guidelines.

All dose adjustments presume that the toxicity is determined by the investigator to be possibly, probably, or definitely related to blinatumomab, pembrolizumab, or both. Withholding the dose and dose adjustments should not occur if toxicity is felt unlikely to be or definitely not related to study blinatumomab, pembrolizumab, or both.

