6.2 Procedures During Treatment

Lumbar puncture with intrathecal methotrexate 15 mg day 29 + 8 days during cycles 1-4 and day 38 + 8 of cycle 5 for total of 6 doses including dose given at screening. CSF studies with each lumbar puncture: Cell count with differential, cytology, and flow cytometry.

Adverse events and concomitant medications to be collected continuously while on study.

Cycle 1

Day 1

Collection of Serum Cytokine Assay samples (See **Section 6.5**) prior to blinatumomab

Administration of Blinatumomab 9 mcg/d CIV on days 1-7 (hospital admission required per section 5.1.3)

Physical exam, performance status, vital signs, weight

Vital signs (heart rate and oxygen saturation) to be monitored continuously and full vital signs (temperature, heart rate, blood pressure, respiratory rate, and oxygen saturation) every 4 hours during at least the initial 72 hours of blinatumomab therapy, for 72 hours after all restart or step-up doses, and for at least the initial 72 hours following the first (Cycle 1, Day 15).

Labs: CBC with differential, CMP (sodium, potassium, chloride, bicarbonate, BUN, creatinine, glucose, calcium, total bilirubin, AST, ALT, alkaline phosphatase), direct bilirubin

Adverse Event Assessment

Concomitant Medications

Day 2

Collection of Serum Cytokine Assay Samples 24 hours +/- 2 hour after start of blinatumomab (See **Section 6.5**)

Day 3

Collection of Serum Cytokine Assay samples 48 hours +/- 2 hours after start of blinatumomab (See **Section 6.5**)

Day 8

Collection of Serum Cytokine Assay samples (See **Section 6.5**) prior to increase in blinatumomab dose

Start administration of Blinatumomab 28 mcg/d CIV days 8-28

Day 9

Collection of Serum Cytokine Assay Samples 24 hours +/- 2 hour after start of blinatumomab 28 mcg/day (See **Section 6.5**)

Day 10

Collection of Serum Cytokine Assay samples 48 hours +/- 2 hours after start of blinatumomab 28 mcg/day (See **Section 6.5**)

Day 14

Labs: CBC with differential, CMP (sodium, potassium, chloride, bicarbonate, BUN, creatinine, glucose, calcium, total bilirubin, AST, ALT, alkaline phosphatase), direct bilirubin, amylase and lipase

Procedures: Bone marrow aspiration and biopsy. Send for standard histology, flow cytometry, cytogenetics (karyotype and *in situ* hybridization for previously documented abnormalities required, other testing per institutional standard of care) and quantitative PCR for BCR-ABL1 p190 and/or p210 if previously positive.

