8.1 Adverse Event Monitoring

Adverse event data collection and reporting, which are required as part of every clinical trial, are done to ensure the safety of subjects enrolled in the studies as well as those who will enroll in future studies using similar agents. Adverse events are reported in a routine manner at scheduled times during a trial. Additionally, certain adverse events must be reported in an expedited manner to allow for optimal monitoring of patient safety and care.

As far as possible, each adverse event should be evaluated to determine:

- duration (start and end dates)
- severity (grade)
- seriousness
- relationship to study agent
- action taken (i.e., none, study agent modification, medical intervention)
- outcome (i.e., resolved without sequelae, resolved with sequelae, ongoing)

Adverse events monitoring begins after initiation of study treatment and ends 30 days following the last administration of study treatment or study discontinuation/termination, whichever is earlier.

Adverse events may also occur in screened subjects during any pre-allocation baseline period as a result of a protocol-specified intervention, including washout or discontinuation of usual therapy, diet, placebo treatment or a procedure.

Progression of the cancer under study is not considered an adverse event unless it is considered to be drug related by the investigator.

All adverse events will be recorded from the time the consent form is signed through 30 days following cessation of treatment and at each examination on the Adverse Event case report forms/worksheets. The reporting timeframe for adverse events meeting any serious criteria is described in **Section 8.3**.

All patients experiencing an adverse event, regardless of its relationship to study drug {or at least possibly related to the drug}, will be monitored until:

- the adverse event resolves or the symptoms or signs that constitute the adverse event return to baseline;
- any clinically significant abnormal laboratory values have returned to baseline;
- there is a satisfactory explanation other than the study drug for the changes observed; or
- death

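### The adverse-event endpoint is labelled safety of the combination, but as written it also counts the 14-day blinatumomab-only lead-in and any patient who never receives pembrolizumab

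*Combined protocol and SAP*

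**What the plan says.** The endpoint, section 3.2.7: "Safety and tolerability of blinatumomab in combination with pembrolizumab will be defined by treatment-emergent Grade 2-5 adverse events". The same sentence grades by CTCAE and keeps only events judged related to study therapy; it does not say which drug.

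The analysis set, section 7.2: "Analyses will be performed for all patients having received at least one dose of study drug".

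The start of counting, section 7.1.1: "All patients will be evaluable for toxicity from the time of their first treatment on study". Section 5.7 agrees: "Any patient who receives treatment on this protocol will be evaluable for toxicity". So does section 8.1: "Adverse events monitoring begins after initiation of study treatment". Another sentence in 8.1 starts recording at consent. The two should be reconciled, but both take in Days 1-14.

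The schedule: section 6.2 lists for Cycle 1 Day 1 "Administration of Blinatumomab 9 mcg/d CIV on days 1-7", with the step-up on Day 8. The DLT definition in section 5.1.1 fixes when pembrolizumab begins: it covers events "occurring within 42 days of the first dose of pembrolizumab on Day 15 of Cycle 1".

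The analysis, section 10.5.2: adverse-event rates are to be summarised descriptively. No section gives a split by period or a pembrolizumab-exposed safety set for these rates.

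**The concern.** Objective 2.2.7 asks how safe and tolerable the two drugs are together. A rate that starts on Day 1 answers a different question: how toxic is the whole regimen, including two weeks of blinatumomab alone?

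The difference could matter here. Those two weeks contain the start of blinatumomab and its dose step-up. Section 1.4.2 reports cytokine peaks 8 to 16 hours after the start in an MRD-positive population, and more severe, longer elevation at high disease burden. This trial enrols only patients with more than 50% marrow blasts. Cytokine release or neurotoxicity in that window would count toward the combination although no pembrolizumab had been given. The relatedness filter does not remove such events, because blinatumomab is itself study therapy.

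There is also a route into the denominator. The tables in section 5.7.1 take a patient off protocol therapy for certain cytokine-release and neurologic events. If one occurs before Day 15, that patient is never exposed to pembrolizumab but stays in the safety set. Section 10.4, in contrast, bases response, RFS and OS on patients who receive the combination from Day 15. Benefit and risk could then rest on different patients.

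**Working it through.** **Is there a plan figure to reproduce?** Not on this point: the documents state no adverse-event rate. The Simon design in section 10.5.1 reproduces (type I error 0.0499, power 0.8014, early termination 0.880) and does not depend on the safety set.

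**How the plan treats exposure elsewhere**

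| Item | Starts from | Patients | Relatedness |
|---|---|---|---|
| DLT definition (5.1.1, 5.1.4) | First pembrolizumab dose | See Stage 1 row | At least probable, to pembrolizumab or the two together |
| Stage 1 DLT set (10.4) | Day 15 | Combination-exposed | As above |
| Response, RFS, OS (10.4) | – | Combination-exposed from Day 15 | – |
| Adverse-event endpoint (3.2.7, 7.1.1, 7.2) | First treatment, Day 1 | Anyone treated | To study therapy as a whole |

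Only the last row, which carries the combination's label, ignores pembrolizumab exposure. (The DLT window is 42 days in section 5.1.1 and 28 days in section 10.4. These need reconciling, but both start on Day 15.)

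**Length of the two periods.** The lead-in is 15 − 1 = 14 days. Five 42-day cycles give 5 × 42 = 210 days, leaving 210 − 14 = 196 days from Day 15.

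**Illustration; the inputs below are assumptions.**
- Pembrolizumab-exposed patients: 24. This is the number section 10.5.1 plans as evaluable for the combination.
- u: patients who receive blinatumomab only, 0 to 6.
- q: chance of a counted event before Day 15, 0.10 to 0.50.
- c: independent chance of a counted event from Day 15, 0.20 or 0.40, whether or not the patient had one earlier.

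Rate in exposed patients from Day 15: c.

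Rate in all treated patients from Day 1: [24 × (1 − (1 − q)(1 − c)) + u × q] / (24 + u).

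Worked case, u = 0, q = 0.10, c = 0.20: 1 − 0.90 × 0.80 = 0.28.

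Worked case, u = 6, q = 0.50, c = 0.20: (24 × 0.60 + 6 × 0.50) / 30 = 17.4 / 30 = 0.58.

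| Rate from Day 15, exposed (c) | All treated from Day 1, u = 0 | All treated from Day 1, u = 6 |
|---|---|---|
| 20% | 28% to 60% | 24% to 58% |
| 40% | 46% to 70% | 39% to 66% |

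Each range runs from q = 0.10 to q = 0.50. With u = 0 the excess is q × (1 − c), so the rate rises even if every patient reaches Day 15.

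**Dilution.** For an event that can occur only after pembrolizumab, the all-treated rate is 24c / (24 + u). With c = 0.20, 24c = 4.8:
- u = 2: 4.8 / 26 = 18.5%
- u = 4: 4.8 / 28 = 17.1%
- u = 6: 4.8 / 30 = 16.0%

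The two effects pull in opposite directions. At u = 6, q = 0.10, c = 0.40 they nearly cancel: (24 × 0.46 + 0.6) / 30 = 38.8%, against 40%.

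**The case against.** An all-treated safety set counted from first dose is standard. The regimen under test includes the lead-in, so describing its toxicity from Day 1 is legitimate. That stands: the table should be kept. What is missing is a second presentation that matches the label.

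Section 7.2 names an analysis set and section 7.1.1 defines evaluability; neither says that all periods go into a single rate, and section 10.5.2 leaves the layout open. That is fair. An analyst could split the table without breaching the plan. But the only starting point the plan gives is first treatment, and nothing requires a split.

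The number of unexposed patients may be small or zero. Progression is a reason to stop only after Day 15 (sections 5.1.3 and 5.8), which limits early loss. This stands, and it makes dilution the lesser issue. It does not remove the inflation, which needs no unexposed patients.

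Three stronger readings are tempting and should be set aside.
- A reader might infer that the safety gate is contaminated. It is not: the DLT definition counts from the first pembrolizumab dose and requires relatedness to pembrolizumab or the two drugs together, and the Stage 1 set is limited to combination-exposed patients.
- A reader might infer that the before-and-after comparison within patients is lost. It is only unplanned: section 8.1 asks for start date, grade and relationship for each event. Nor is it the only such contrast, since the cytokine and T-cell studies also compare blinatumomab alone with the combination.
- A reader might expect that comparison to isolate pembrolizumab's effect. It cannot: the periods differ in length (14 days against up to 196), in blinatumomab dose and in disease burden.

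**Conclusion.** The point holds for the secondary adverse-event endpoint only. As written, sections 3.2.7, 7.1.1 and 7.2 put blinatumomab-only events from Days 1-14, and any patients never given pembrolizumab, into a rate labelled as the combination's.

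Its size is unknown. The percentages above rest on assumed event chances, independence between the two periods, and an assumed number of early stoppers. They show that common early events would raise the rate and that a wider denominator would lower it for pembrolizumab-specific events, with dilution the smaller effect over most of the range. They do not estimate what this trial will report. A reader might take 24 as the number treated and subtract early stoppers from it. The plan does not support that: section 10.5.1 sets 24 as the number evaluable for the combination, so at full accrual any unexposed patients come on top.

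No test, stopping rule or primary result changes. This is an inexpensive improvement to how objective 2.2.7 is answered.

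**What to change.** Keep the all-treated, from-first-dose table and label it the whole-regimen summary. In sections 3.2.7, 7.2 and 10.5.2, add two descriptive tables by date of event onset:

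- (a) from the first blinatumomab dose to before the first pembrolizumab dose, in all treated patients;
- (b) from the first pembrolizumab dose, in pembrolizumab-exposed patients only. Count a patient here if an event type recurs after Day 15, even if it first appeared earlier.

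State both denominators. Show all-cause events by grade beside those judged related to study therapy. Add one sentence saying that comparison of the two periods is descriptive only, because duration, blinatumomab dose and disease burden differ.

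The cost is a text change and the extra tables. Section 8.1 already collects start date, grade and relationship, so no new data, visits or patients are needed.
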